#### Study Glossary

Abbreviation or Term	Definition/Explanation
 FDG-PET	18-fluorodeoxyglucose-positron emission tomography
AE	adverse event
ALP	alkaline phosphatase
ALT	alanine aminotransferase
ANC	absolute neutrophil count
AST	aspartate aminotransferase
AUC	area under the concentration-time curve
BLRM	Bayesian logistic regression model
BM	bone marrow
B-NHL	B-cell Non-Hodgkin Lymphoma
CAR	chimeric antigen-receptor
CBC	complete blood count
C max	maximum concentration
Cmin	minimum concentration
CMR	complete metabolic response
CNS	central nervous system
COO	cell-of-origin
CR	complete response
CRF	case report form
CRP	C-reactive protein
CRS	cytokine release syndrome
CSF	cerebro spinal fluid
СТ	computed tomography
CTCAE	Common Terminology Criteria for Adverse Events
ctDNA	circulating tumor DNA
DILI	drug induced liver injury
DLBCL	diffuse large B-cell lymphoma
DLRM	Dose level review team meeting
DLRT	dose level review team
DLT	dose limiting toxicities
DOR	duration of response
EC 50	half maximal effective concentration
EC 90	effective concentration leading to 90% response
EDC	electronic data capture
ECG	Electrocardiogram
ECOG	Eastern Cooperative Oncology Group
eCRF	electronic case report form

Abbreviation or Term	Definition/Explanation
End of Follow-up	defined as when the last subject completes the last protocol-specified assessment in the study
End of Study for Individual Subject	defined as the last day that protocol-specified procedures are conducted for an individual subject (ie, the date the subject withdraws full consent from the study, completes the safety follow-up visit or long-term follow up [whichever is later] or death).
End of Study (primary completion)	the time when the last subject is assessed or receives an intervention for the purposes of final collection of data for the primary analysis
End of Study (end of trial)	the time when the last subject is assessed or receives an intervention for evaluation in the study.
End of Treatment	defined as the last assessment for the protocol-specified treatment phase of the study for an individual subject
FDA	Food and Drug Administration
FIH	first-in-human
FISH	fluorescent in situ hybridization
FSH	follicle stimulating hormone
GCP	good clinical practice
G-CSF	granulocyte colony-stimulating factor
GM-CSF	granulocyte macrophage colony-stimulating factor
HepBsAg	hepatitis B surface antigen
HepCAb	hepatitis C virus antibody
HIV	human immunodeficiency virus

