#### 3.5 Estimated Study Duration

#### 3.5.1 Study Duration for Subjects

It is anticipated that an individual subject will participate in the study for up to 2 years.

This includes a screening period lasting up to 21 days, a treatment period lasting for a median of approximately 8 months, a Safety follow-up visit 30 (+7) days after the last dose of AMG 562, and a follow-up period lasting up to 2 years from the first dose of AMG 562.

The actual duration for individual subjects will vary depending upon tolerability of AMG 562, evidence of clinical progression, and willingness to participate in the study. End of study (EOS) for an individual subject is defined as the date of the final study visit

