- 218. Males and females of reproductive potential who are unwilling to practice highly effective method(s) of birth control while on study through 110 days (females) and 170 days (males) after receiving the last dose of study drug. Highly effective methods of birth control include sexual abstinence (males, females); vasectomy; bilateral tubal ligation/occlusion; or a condom with spermicide (males) in combination with hormonal birth control or intrauterine device (IUD) (females)
- 219. Females who are lactating/breastfeeding or who plan to breastfeed while on study through 110 days after receiving the last dose of study drug
- 220. Females with a positive pregnancy test
- 221. Females planning to become pregnant while on study through 110 days after receiving the last dose of study drug
- 222. Males who are unwilling to abstain from sperm donation while on study through 170 days after receiving the last dose of study drug
- 223. Subjects likely to not be available to complete all protocol- required study visits or precedures including BM aspirates/biopsies, and/or to comply with all required study procedures to the best of the subject and investigator's knowledge
- 224. History or evidence of any other clinically-relevant concurrent disorder, condition or disease (eq, symptomatic congestive heart failure, unstable angia pectoris, cardiac arrythmia requiring therapy at time of screening) with the exception of those outlined above that, in the opinion of the investigator or Amgen Medical Monitor, if consulted, would not pose a risk to subject safety or interfere with the study evaluation, procedures or completion.

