- DLT (separate guidance for CRS, IRR and Neurotoxicity) or other unmanageable toxicity unless a subject has a clear clinical benefit from treatment, the toxicity has resolved to grade ≤ 1 or baseline and after consultation with the sponsor
- in case of grade 4 non-hematologic adverse event
- grade 3 neurotoxicity needing more than 7 days after treatment interruption to resolve to grade ≤1
- Grade 4 neurotoxicity
- Grade ≥ 3 seizure
- In case of occurrence of more than one seizure of grade ≤ 2
- treatment interruption: if the subject misses at least 2 consecutive doses due to serious adverse events/adverse events
- possible DILI requiring permanent withholding as per Section 6.4
- subjects who require more than 1 dose reduction
- clinically relevant disease progression
- relapse of disease subsequent to response on protocol treatment
- occurrence or progression of a medical condition which in the opinion of the investigator should preclude further participation of the subject in the study
- administration of relevant non-permitted concomitant medications
- requirement for alternative therapy
- subject's request
- subject or investigator not compliant with the study protocol

For grading of events, refer to Section 9.2.2.1.

Females who become pregnant while on study through 120 days after receiving the last dose of study drug will not receive subsequent scheduled doses and will be followed for safety until the EOS visit.

Males with pregnant partners or whose partners become pregnant while the subject is on study through 180 days after receiving the last dose of study drug must practice sexual abstinence or use a condom while on study through 180 days after receiving the last dose of study drug.

All reasons for treatment discontinuation should be clearly and comprehensively documented in the eCRF. If a subject has not continued to present for study visits, the investigator should determine the reason and circumstances as completely and accurately as possible.

In any case of premature treatment discontinuation, the investigator should make every effort to perform all examinations scheduled for the EOT.

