#### 7.2.5 End of Study

End of study is defined as the date of the final study visit (eg, LTFU) when assessments and/or procedures are performed.

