# 9.3 Pregnancy and Lactation Reporting

If a female subject becomes pregnant, or a male subject fathers a child, while the subject is taking protocol-required therapies, report the pregnancy to Amgen Global Patient Safety as specified below.

In addition to reporting any pregnancies occurring during the study, Investigators should report pregnancies that occur through 110 days after the last dose of AMG 562 or in a male subject's female partner through 110 days after the last dose of AMG 562.

The pregnancy should be reported to Amgen Global Patient Safety within 24 hours of the Investigator's knowledge of the pregnancy. Report a pregnancy on the Pregnancy Notification Worksheet (Appendix C). Amgen Global Patient Safety will follow-up with the Investigator regarding additional information that may be requested.

If a female subject becomes pregnant during the study, the Investigator should attempt to obtain information regarding the birth outcome and health of the infant.

If the outcome of the pregnancy meets a criterion for immediate classification as a Serious Adverse Event (eg, female subject experiences a spontaneous abortion, stillbirth, or neonatal death or there is a fetal or neonatal congenital anomaly) the Investigator will report the event as a Serious Adverse Event.

If a female breastfeeds while taking protocol-required therapies report the lactation case to Amgen as specified below.

In addition to reporting a lactation case during the study, Investigators should report lactation cases that occur through 120 days after the last dose of protocol-required therapies.

Any lactation case should be reported to Amgen Global Patient Safety within 24 hours of the Investigator's knowledge of event. Report a lactation case on the Lactation Notification Worksheet (Appendix C). Amgen Global Patient Safety will follow-up with the Investigator regarding additional information that may be requested.

If a male subject's female partner becomes pregnant, the Investigator should discuss obtaining information regarding the birth outcome and health of the infant from the pregnant partner.

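### Section 9.3 applies the 110-day female window to partner pregnancies, short of the protocol's own 170- or 180-day male window for men whose participation ends before that window closes

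*Protocol*

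**What the plan says.** Protocol Section 9.3 sets two reporting periods. One is open: "In addition to reporting any pregnancies occurring during the study". The other is a limit counted from the last dose: 110 days for pregnancies in general and, named separately, 110 days for a male subject's "female partner through 110 days after the last dose of AMG 562".

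Elsewhere the protocol separates the sexes:

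- Section 4.2, exclusion 218 (contraception): "through 110 days (females) and 170 days (males) after receiving the last dose of study drug".
- Section 4.2, exclusion 222: men must be willing to "abstain from sperm donation while on study through 170 days after receiving the last dose of study drug".
- Section 6.2.1.4.4 requires abstinence or condom use of men "whose partners become pregnant while the subject is on study through 180 days after receiving the last dose of study drug". The same section uses 120 days for women.

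Two further points decide who is affected. The Study Glossary ends an individual's study at "the date the subject withdraws full consent from the study, completes the safety follow-up visit or long-term follow up [whichever is later] or death", and Section 7.2.5 likewise runs it to the final visit. Section 7.2.4 caps follow-up at 2 years from the first dose. The Glossary and Section 3.5.2 also define a trial-level end of study, at the last subject's last visit. Section 9.3 does not say which meaning applies.

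**The concern.** Section 9.3 treats a male subject's partner as a separate case and then gives her the female number. The protocol asks men to take precautions for 170 days and anticipates partner pregnancies out to 180 days, yet its explicit post-dose duty to report them stops at 110. Neither document gives a reason for a shorter male reporting window.

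What is at stake is safety information. In a first-in-human study, a site following 9.3 literally need not report a partner pregnancy that arises between day 111 and day 170 (or 180) after the last dose in a man who is no longer on study. Section 9.2.2.3 is not a clear backstop: outside the required period there is no duty to monitor for serious adverse events, and their reporting is optional unless local rules require it.

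**Working it through.** The plan states no figure to reproduce. The check is day arithmetic.

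**Inputs**

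- Partner reporting window: 110 days (Section 9.3).
- Male window M: 170 days (exclusions 218 and 222) or 180 days (Section 6.2.1.4.4).
- Follow-up cap: 2 years from first dose (Section 7.2.4), taken as 730 days.
- Expected treatment: "a treatment period lasting for a median of approximately 8 months" (Section 3.5.1), about 8 × 30.4 = 243 days.
- Late last doses are possible. Section 6.2.1.1 allows treatment while the subject benefits, and Section 3.1 (Treatment Holiday) allows subjects still in complete remission at 12 months to continue until progression.

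**Formula**

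Let D be the day of last dose and E the day the man's study participation ends. Days covered after the last dose = max(110, E − D), because pregnancies during the study are reportable regardless.

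Gap = max(0, M − max(110, E − D)).

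The largest possible gap is 170 − 110 = 60 days, or 180 − 110 = 70 days.

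**Men followed to the cap (E = 730, individual reading of the study period)**

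| Last dose, day D | E − D | Days covered | Gap, M = 170 | Gap, M = 180 |
|---|---|---|---|---|
| 243 (median) | 487 | 487 | 0 | 0 |
| 550 | 180 | 180 | 0 | 0 |
| 560 | 170 | 170 | 0 | 10 |
| 590 | 140 | 140 | 30 | 40 |
| 620 | 110 | 110 | 60 | 70 |

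The gap opens when D + M > 730, that is after day 730 − 170 = 560, or after day 730 − 180 = 550. It is full from day 620 and stays full for later last doses. The safety visit, 30 to 37 days after the last dose, falls inside the 110 days and adds nothing.

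**Men who leave early (illustrative exit times)**

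| Exit, days after last dose | Days covered | Gap, M = 170 | Gap, M = 180 |
|---|---|---|---|
| 30 | 110 | 60 | 70 |
| 140 | 140 | 30 | 40 |
| 170 | 170 | 0 | 10 |
| 180 | 180 | 0 | 0 |

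**Trial-level reading**

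If the study period in 9.3 runs to the last subject's last visit, E becomes that date. Men who reach their own 2 years while others are still followed remain covered, so fewer men have a gap and day 560 is no longer the general threshold.

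**After the fix**

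Replacing 110 by M gives max(0, M − max(M, E − D)) = 0 for every D and E.

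**The case against.** Several points on the other side stand in whole or in part.

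- **The male reporting window is inferred.** No text says that it must equal the contraception window, and the 180-day sentence in Section 6.2.1.4.4 is about abstinence and condoms, not reporting. This is correct. The point rests on internal inconsistency: 9.3 singles men out and then uses the figure that Section 4.2 reserves for women.
- **A longer window cannot help every early leaver.** Section 8.3.2 lists sponsor decision, withdrawal of consent, death and loss to follow-up as reasons for removal. A man lost to follow-up cannot be reached under either figure, and one who withdraws consent has ended participation (Section 8.1). Stopping drug is not leaving: Section 8.1 says that such subjects should not be removed automatically. The edit mainly serves men removed early who can still be contacted, clearly those removed by sponsor decision.
- **There is a partial backstop.** Section 9.3 ends by asking the investigator to discuss obtaining birth-outcome information when a partner becomes pregnant, with no time limit. This softens the gap but does not replace notification to the sponsor.
- **Few men are exposed.** Men must be willing to use highly effective contraception through 170 days, and a last dose after day 560 is more than twice the expected median of about 243 days.
- **The study has stopped.** SAP Sections 1, 7.2 and 10 describe early discontinuation with one subject ongoing. The sex of that subject is not stated.

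A reader might infer that every man loses 60 days of reporting. The documents do not support that, because pregnancies during the study are reportable and individual participation normally runs well past 170 days after the last dose.

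**Conclusion.** The inconsistency is genuine and minor. Section 9.3 is up to 60 days short of the 170-day male window, or 70 days short of the 180-day figure. This matters only for men whose participation ends before that window closes: those removed early but still contactable and, on the individual reading of the study period, those last dosed after about day 560 (or 550).

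The day thresholds assume a 730-day cap and that individual reading. The trial-level reading is also open and affects fewer men, so day 560 should not be read as a firm cut-off. The documents do not say how many men fall in either group, or whether termination by the sponsor ended anyone's participation soon after his last dose.

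No analysis, dose decision or stopping rule depends on the number. Nothing shows that 110 days for partners was chosen deliberately. With 110, 120, 170 and 180 days all in use, and 9.3 itself using 120 for lactation, it looks like one set of figures that was not harmonised.

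**What to change.** In Section 9.3, change the partner-pregnancy reporting window from 110 to 170 days after the last dose, or to 180 if the sponsor adopts the Section 6.2.1.4.4 figure. In the same edit, settle 110 against 120 days for women and 170 against 180 for men across Sections 4.2, 6.2.1.4.4 and 9.3. It would also help to state whether reporting during the study refers to the individual's participation or to the whole trial.

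If no further amendment is planned, a short clarification to sites covering any man still inside his window would serve. The cost is one number plus the harmonisation, and at most 60 (or 70) further days of event-driven reporting for each man affected.

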### 10. STATISTICAL CONSIDERATIONS

#### 10.1 Study Endpoints, Analysis Sets, and Covariates

10.1.1 Study Endpoints

#### Primary Endpoint:

 Safety: Incidence of dose limiting toxicities (DLTs), treatment-emergent adverse events, treatment-related adverse events, disease-related events and clinically-significant changes in vital signs, physical examinations, electrocardiograms (ECG) and clinical laboratory tests

#### Secondary Endpoints:

 AMG 562 PK parameters including, but not limited to, maximum concentration (Cmax), minimum concentration (Cmin), time of maximum concentration (Tmax), area under the concentration-time curve (AUC), and if feasible, half-life (t1/2)

- Efficacy parameters:
  - ORR according to Lugano classification
  - Best overall response by category (response terminology reflects the response criteria used. The Lugano Classification response definitions for PET-CT evaluations of FDG-avid lymphomas uses the terminology CMR, PMR, NMR, or PMD. Corresponding designations from earlier response criteria include CR, PR, SD, or PD.)
  - Duration of response (DOR)
  - Progression free survival (PFS)
  - Overall survival (OS)

# **Exploratory Endpoints:**

• Incidence of anti-AMG 562 antibody formation

# 10.1.2 Analysis Sets

The analysis of all endpoints, unless noted otherwise, will be conducted on the Safety Analysis Set defined as all subjects that are enrolled and receive at least 1 dose of AMG 562.

The analysis of DLT will be conducted on the DLT Analysis Set defined as all subjects who are DLT-evaluable (see Section 6.2.1.3). DLT-evaluable subjects are those who 1) experienced DLTs or 2) completed DLT observational period and did not experience DLTs

The PK Analysis Set will contain all subjects who have received at least 1 dose of AMG 562 and have at least 1 PK sample collected. These subjects will be evaluated for PK analysis unless the number of data points required for analysis is not enough, or significant protocol deviations have affected the data, or if key dosing or sampling information is missing.

### 10.1.3 Covariates and Subgroups

The following subgroups will be used summarized safety data in part 2 of dose expansion:

- Age
  - age group: <65, ≥65; and <75, ≥75
- Sex: Male, Female
- Race
  - American Indian or Alaska Native
  - Asian
  - Black (or African American)
  - Native Hawaiian or Other Pacific Islander
  - White
  - Other
- Geographic region
  - US/Canada
  - Europe
  - Rest of the world
  - Disease state:
    - Transformed disease
    - o Primary refractory disease
    - o Refractory to last treatment
    - o GCB versus non-GCB (Hans algorithm)
    - o Double or Triple hit, vs non-double or triple hit, by FISH
  - Prior treatments
    - o Autologous HSCT
    - CD19-targeted treatment

#### 10.1.4 Handling of Missing and Incomplete Data

For efficacy data of overall response, subjects without tumor response assessments will be considered as nonresponders. Otherwise, only nonmissing data will be analyzed.

Ineligible subjects and subjects enrolled in Part 1 who are not DLT evaluable may be replaced.

#### 10.2 Sample Size Considerations

It is anticipated that approximately 85 subjects will be enrolled in this study. Approximately 30 subjects will be enrolled in the dose escalation cohorts and up to 55 additional subjects will be enrolled in the dose expansion cohort. The sample size in

the dose escalation is based on practical considerations and is consistent with conventional oncology studies with the objective to estimate the MTD. With 3 subjects per cohort, there is a 27-70% probability of observing at least one DLT if the true DLT rate is 10-33% and with 4 subjects per cohort, there is a 34-80% probability.

In the dose expansion cohort, a subject number of 55 will provide a 43% probability of observing at least one adverse event with 1% incidence rate and 94% probability of observing at least one adverse event with 5% incidence rate. An exact 90% binomial confidence interval (CI) will be provided for overall response rate. With the 55 subjects and 40% overall response rate, the expected two-sided 90% CI would be 29% to 52%.

# 10.3 Adaptive Design

Details of the adaptive BLRM design are described in Appendix J.

# 10.4 Planned Analyses

### 10.4.1 Interim Analyses

In the dose escalation part, safety data will be reviewed on an ongoing basis. Based on accumulating toxicity information, BLRM will be used to make dosing recommendations. In dose level review team meetings (DLRMs), Amgen, in consultation with the site investigators, will review the BLRM recommended dose level and will review all available cumulative data by cohort prior to making dose escalation decisions. As a sensitivity analysis, a one-parameter Continual Reassessment Method model may be used to estimate the dose-toxicity relationship to help making dose escalation decisions. Adverse events and DLTs observed in all subjects will be evaluated continually and fully integrated into all DLRMs and considered in all enrollment and dosing decisions.

The clinical activity of AMG 562 in the dose expansion part will be examined using a Bayesian predictive probability design. If the posterior probability is more than 85% that the ORR is 40% or less, then this is considered insufficient anti-lymphoma activity. If the ORR is too low, enrollment may be terminated early due to insufficient anti-lymphoma activity. The guidelines for futility due to insufficient efficacy assuming a prior beta distribution (0.8, 1.2) are presented in Table 15. The operating characteristics in Table 16 provide the probability of stopping the trial early for given hypothetical true ORR rates whereas the stopping criteria in Table 15 are based on situations where the empirical evidence would result in a posterior probability of  $\geq$ 85% that the true ORR rate is  $\leq$  40%.

The DLRT will be convened in the dose expansion part of the study to review efficacy data (with recruitment ongoing) after the first 15 subjects are enrolled and have had the opportunity to receive at least five weeks of treatment (with recruitment ongoing).

Number of Treated Subjects	Efficacy Futility Guideline					
15	4 or fewer responders					
20	5 or fewer responders					
25	7 or fewer responders					
30	9 or fewer responders					
35	11 or fewer responders					
40	12 or fewer responders					
45	14 or fewer responders					
50	16 or fewer responders					
55	Trial will stop					

 Table 15. Guideline for Insufficient Efficacy

Table 16.	Operating	Characteristics for futi	ility With Batch Size of 5 Subject	S
	oporading			

True ORR Rate	Probability of Stopping Early for Futility	Average Sample Size
0.25	95%	21
0.30	81%	27
0.35	59%	36
0.40	36%	43
0.45	18%	49
0.50	8%	52
0.55	3%	54

Additionally, the DLRT will review safety data and conduct evaluations of the ongoing DLT rate to assess if the threshold for early trial termination has been reached.

The stopping rules use a Bayesian approach to terminate the study if the posterior probability that the DLT rate is greater than 33% is > 90%. The stopping boundaries assuming a prior beta distribution (0.66, 1.33) are presented in Table 17. The operating characteristics in Table 18 provide the probability of stopping the trial early for given hypothetical true DLT rates whereas the stopping criteria in Table 17 are based on situations where the empirical evidence would result in a posterior probability of  $\geq$  90% that the true DLT rate is  $\geq$  33%. The evaluations could occur more frequently if necessary to address emerging safety concerns.

Number of DLT Evaluable Subjects	Stop Study If Observing These Many DLTs
10	≥ 6
15	≥ 8
20	≥ 10
25	≥ 12
30	≥ 14
35	≥ 16
40	≥18
45	≥ 20
50	≥ 21
55	Trial will stop

Table 17. Stopping Boundaries

Table 18. Operating Characteristics for stopping early With Batch Size of
5 Subjects

True DLT Rate	Probability of Stopping Early	Average Sample Size
0.20	1%	55
0.25	4%	53
0.3	13%	51
0.33	22%	48
0.35	31%	45
0.40	56%	37
0.45	79%	29

